1.3 Sample Size

NAV3-33 is sized with respect to achieving specified goals in the co-primary endpoints of sensitivity and specificity of $\Delta TUV_{global[5w]}$ with bucketing. Sensitivity and specificity require knowledge of the patient's clinical status at Week 24, and so hypothesis testing will be performed after classification. The value of $\Delta TUV_{global[5w]}$ necessary to predict response vs. non-response and the value of $TUV_{global[5w]}$ necessary to predict response vs. non-response and the value of TUV_{global[b]} at baseline necessary to predict non-response will be determined in advance. The classification procedure occurs in two stages, following the baseline image acquisition and (possibly) following the 5 week image acquisition and calculation of $\Delta TUV_{global[5w]}$. After the baseline imaging, patients whose TUV_{global[5w]} is available, patients whose TUV_{global[b]} is ≥ 5 and D% is $\leq -10\%$ are predicted to be responders. All other patients are predicted to be non-responders. The Week 24 ACR50 will be used as the primary determination of clinical response for the reference standard

The hypotheses for the co-primary endpoints to be tested are:

$$H_{O1}: \pi_{Sp} \le 0.8$$

 $H_{A1}: \pi_{Sp} > 0.8;$

And

 $H_{02}: \pi_{Se} \le 0.65$ $H_{A2}: \pi_{Se} > 0.65.$

In the above π_{Sp} represents the true specificity of the classification procedure and π_{Se} represents the true sensitivity of the classification procedure when used to predict the outcome of the anti-TNF α bDMARD inhibitor therapy at 24 weeks. An overall two-tailed Type I error rate of 0.05 (one-tailed 0.025) was used without adjusting for multiple endpoints, as both co-primary endpoints must be achieved in order to have a successful study. If the actual specificity is 0.92 and the actual sensitivity is 0.8, and if an exact binomial test is used to test the above hypotheses, a total of 98 clinical non-responders and 100 clinical responders are needed for 90% power of the individual tests. That is, a minimum of 198 total patients is needed. This applies to a single reader.

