2.3 Missing Data Conventions

In the statistical analysis of the primary efficacy endpoints of the study, missing data will be handled according to the following table of missing data scenarios:

Variable	Scenario	Primary Imputation Rule	Secondary Imputation Rule
Clinical Status at Week 24	Patient discontinued anti-TNFα therapy prior to Week 24 due to non- response to therapy	Patient classified as a clinical non- responder	N/Ă

Clinical Status at Week 24	Patient discontinued study for reasons not attributable to non-response	Clinical status set to missing	Impute mean clinical response*
TUV Prediction	Patient has TUV _{global[b]} that is ≥ 5 but is missing week 5 imaging data	Impute mean prediction**	Prediction is Y (patient has improved)
TUV Prediction	Patient is missing TUV _{global[b]}	Prediction set to missing	N/A

*Mean clinical response will be calculated as follows: calculate the proportion of unique patients whose clinical status is Y (patient is a clinical responder), randomly allocate this proportion of "Y" to the missing clinical status at week 24 values. Assign all other missing clinical status values "N" (patient is clinical non-responder).

**Mean prediction will be calculated as follows: using the patients for whom $TUV_{global[b]} \ge 5$, calculate the proportion whose TUV prediction is Y (patient has improved), randomly allocate this proportion of "Y" to the missing TUV predictions. Assign all other missing TUV predictions "N" (patient has not improved).

To assess the appropriateness of the missing data conventions for clinical status at week 24 and TUV prediction using mean imputation, tipping point analyses will be performed. Specifically, 95% confidence intervals for sensitivity and specificity will be plotted against increasing proportions of missing values imputed as "Y" to see at what point the conclusion of the study is reversed.

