XXXXX	xxx (xxx%)	xxx (xxx%)	xxx (xxx%)	xxx (xxx%)				
XXXXX	xxx (xxx%)	xxx (xxx%)	xxx (xxx%)	xxx (xxx%)				

Table 52. Vital Signs Summary Statistics Navidea Biopharmaceuticals - Study No. NAV3-33 Safety Population (N=xxx)

Vital Sign		Data						
Parameter (units)	Visit	Typeª	Mean	Std Dev	n	Min	Max	Median
xxxxxxxxx (xxx)	Day 0 Pre-Injection(Baseline)	RAW	XXX	XXX	XXX	XXX	XXX	XXX
	Day 0 Post-Injection	RAW	XXX	XXX	XXX	XXX	XXX	XXX
		CFB	XXX	XXX	XXX	XXX	XXX	XXX
	Week 5 Pre-Injection(Baseline)	RAW	XXX	XXX	XXX	XXX	XXX	XXX
	Week 5 Post-Injection	RAW	XXX	XXX	XXX	XXX	XXX	XXX
		CFB	XXX	XXX	XXX	XXX	XXX	XXX
	Week 12 Pre-Injection(Baseline)	RAW	XXX	XXX	XXX	XXX	XXX	XXX
	Week 12 Post-Injection	RAW	XXX	XXX	XXX	XXX	XXX	XXX
		CFB	XXX	XXX	XXX	XXX	XXX	XXX
	Week 24 Pre-Injection(Baseline)	RAW	XXX	XXX	XXX	XXX	XXX	XXX
	Week 24 Post-Injection	RAW	XXX	XXX	XXX	XXX	XXX	XXX
		CFB	XXX	XXX	XXX	XXX	XXX	XXX

^a RAW = data recorded in database; CFB = change from baseline= (parameter value at the current time point)-(Baseline parameter value). STATKING Clinical Services (DD-MMM-YYYY) Source Program: xxxxxxx.sas

Figure 1. Plot of ATUV_{global} by Imaging Time Point and ACR20 Navidea Biopharmaceuticals - Study No. NAV3-33 ITD Population (N=xxx)

Part 1 of 3: Reader x

Responder status based on ACR20 at each week. STATKING Clinical Services (DD-MMM-YYYY) Source Program: xxxxxx.sas

Figure format repeats for each part and for Figures 2-5. Footnote text will be updated in each figure to correspond to the clinical assessment noted in the title (ACR50, ACR70, CDAI, or DAS28).

Figure 6. Sensitivity Analysis #1 - Tipping Point Analysis to Assess the Appropriateness of Imputation of Clinical Status at Week 24 Navidea Biopharmaceuticals - Study No. NAV3-33 ITD Population (N=xxx)

Part 1 or 2: Sensitivity

Remaining missing week 24 clinical status outcomes imputed as non-responders. Solid horizontal line represents 65% sensitivity. STATKING Clinical Services (DD-MMM-YYYY) Source Program: xxxxxxx.sas

STATKING Clinical Services Version 4.0

Figure 6. Sensitivity Analysis #1 - Tipping Point Analysis to Assess the Appropriateness of Imputation of Clinical Status at Week 24 Navidea Biopharmaceuticals - Study No. NAV3-33 ITD Population (N=xxx)

Part 2 of 2: Specificity

Remaining missing week 24 clinical status outcomes imputed as non-responders. Solid horizontal line represents 80% specificity. STATKING Clinical Services (DD-MMM-YYYY) Source Program: xxxxxxx.sas

Figure format repeats for Figure 7.

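### The tipping-point analysis for missing Week 24 outcomes ignores predicted class, so it understates how robust sensitivity is and never shows missing outcomes that follow the observed PPV and NPV

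*SAP*

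**What the plan says.** SAP 2.3 sorts missing Week 24 outcomes into two kinds. Patients who stopped anti-TNFα therapy because it was not working count as clinical non-responders. Patients who left the study for other reasons have clinical status set to missing under the primary rule. Under the secondary rule they receive a mean clinical response. The footnote defines this by taking the overall proportion of responders and says to "randomly allocate this proportion of" responder codes to the missing values; the rest become non-responders.

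To judge whether the mean-imputation conventions are appropriate, the SAP plans tipping-point analyses in which "95% confidence intervals for sensitivity and specificity will be plotted against increasing proportions of missing values imputed as" responder, to find where the study's conclusion reverses. The Figure 6 shell in Appendix B adds: "Remaining missing week 24 clinical status outcomes imputed as non-responders". Its reference lines are the co-primary criteria: "Solid horizontal line represents 65% sensitivity" and "Solid horizontal line represents 80% specificity". None of these texts mentions the predicted class of the patient whose outcome is imputed.

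**The concern.** Sensitivity and specificity measure how closely prediction and outcome go together. Imputing outcomes without regard to prediction builds in no association among the missing patients. If the test performs as the plan assumes, most patients are predicted non-responders, so most imputed responders land among them and count as false negatives. Sensitivity then falls as the axis moves right, partly because of the imputation scheme.

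A tipping-point analysis should start from a neutral reference and show how far the missing data must depart from it before the conclusion changes. The natural reference is that missing patients respond at the observed rate for their predicted class. The planned axis does not contain that point. A reader could see a reversal near the completers' own response rate and think the result fragile when it is not. The secondary imputation rule uses the same class-blind allocation, so it is not an independent check.

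**Working it through.** **Inputs (SAP 1.3, 2.3 and 4.2.1).** "If the actual specificity is 0.92 and the actual sensitivity is 0.8"; 5 non-responders per responder; 100 responders and 500 non-responders completing; 10% dropout, about 672 enrolled; 95% Clopper-Pearson limits; one-tailed 0.025.

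**Assumptions.** Missing patients have the completers' share of predicted responders. All dropouts have missing outcomes unless stated. One reader. Expected, sometimes fractional, counts go into the limits.

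**1. The plan's own figures.** The SAP states that "a total of 98 clinical non-responders and 100 clinical responders are needed for 90% power of the individual tests". The exact binomial test gives:
- 100 responders: reject at 75 or more correct; level 0.021, power 0.913 at 0.80.
- 98 non-responders: reject at 87 or more; level 0.016, power 0.908 at 0.92.

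These agree. For dropout, 600/0.9 = 667 (67 missing), against the stated 672 (72 missing).

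**2. Completers' table**

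| | Responder | Non-responder | Total |
|---|---|---|---|
| Predicted responder | A = 80 | B = 40 | 120 |
| Predicted non-responder | C = 20 | D = 460 | 480 |

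Predicted-responder share = 120/600 = 20%. PPV = 80/120 = 0.667. 1 - NPV = 20/480 = 0.042. Overall response rate = 100/600 = 1/6.

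**3. Pooled random allocation.** With m missing and pooled proportion p, mp responders are added, 20% of them predicted responders on average:

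Se(p) = (80 + 0.2mp) / (100 + mp)

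- m = 67, p = 1/6: 82.2/111.2 = 0.740, lower limit 0.648.
- m = 72, p = 1/6: 82.4/112 = 0.736, lower limit 0.644.
- m = 72 along the axis: 0.800 at p = 0, 0.641 at 0.5, 0.549 at 1.

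Specificity at m = 72 stays at 0.905 or higher, with lower limit at least 0.878.

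**4. Imputation within predicted class.** At m = 72 the missing are 14.4 predicted responders and 57.6 predicted non-responders.
- Imputed responders: 14.4 × 0.667 = 9.6 and 57.6 × 0.042 = 2.4, total 12. This is the same total as the pooled scheme, which splits it 2.4 and 9.6.
- Se = 89.6/112 = 0.800, lower limit 0.714 (also 0.714 at m = 67).
- Sp = 515.2/560 = 0.920, lower limit 0.894.

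**5. How firm the crossing is at p = 1/6** (imputed responders rounded to whole patients)

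| Missing | Sensitivity | Lower limit |
|---|---|---|
| 30 | 0.771 | 0.679 |
| 40 | 0.761 | 0.669 |
| 50 | 0.756 | 0.663 |
| 60 | 0.745 | 0.654 |
| 67 | 0.741 | 0.649 |
| 72 | 0.736 | 0.644 |

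- With unrounded counts, the limit first falls below 0.65 at about 65 missing.
- At 72 missing with 81/100 observed sensitivity instead of 80/100, it is 0.654 and passes.
- With 198 completers (100 and 98) and an assumed 22 missing, sensitivity is 0.765, lower limit 0.675.
- One patient decides the 67-missing case: 82/111 gives 0.647, 83/111 gives 0.656.
- A single random allocation falls below 0.65 with probability 0.64 at 67 missing and 0.83 at 72.

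**6. Where sensitivity tips.** On the pooled axis, at about 16% (m = 67) or 15% (m = 72), just under 1/6. If missing predicted responders are held at 0.667, sensitivity tips when the rate among missing predicted non-responders, q, brings the lower limit for (80 + 0.2m × 0.667) / (100 + 0.2m × 0.667 + 0.8mq) to 0.65. This gives q of about 22% (m = 67) or 21% (m = 72), roughly five times the reference of 4.2%.

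**The case against.** A reader might infer that the planned figure will show sensitivity failing at the completers' response rate. The documents do not support that. The limit is 0.648 against 0.65, and it needs nearly the full 10% dropout to be missing outcomes. SAP 2.3 counts patients who stopped therapy for non-response as non-responders, and neither document says what share of dropout that is. A modest share removes the crossing, as does one more correctly predicted responder at 72 missing.

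A reader might also infer that the plan omits the missing-at-random case altogether. It does not. The primary complete-case rule gives the same 0.80 when dropout is unrelated to prediction and outcome, and that estimate will be reported. The reference is absent from the figure only.

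Two further points stand. The tipping-point sentence does not say how responder codes are assigned; random allocation comes from the footnote. If it was not intended, the curve is undefined, because sensitivity depends on which patients receive the codes. And it cannot be concluded that readers are missing from Figure 6: the surviving shell text splits it only by sensitivity and specificity, but the graphic is not visible and could show readers within each part.

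Finally, under class-blind allocation the axis is also the rate among missing predicted non-responders, so it gives a usable conservative bound for sensitivity. The plot does not decide success, and its error for sensitivity is pessimistic. That limits the harm. It does not restore the missing reference or remove the distortion.

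**Conclusion.** The point holds as a weakness in a sensitivity analysis and is worth correcting; it is not a flaw in the primary analysis. Because Figure 6 varies one pooled proportion without regard to predicted class, it never represents missing outcomes that follow the observed PPV and 1 - NPV, and it lowers sensitivity as the proportion rises. At the design values the gap in the lower limit is 0.648 against 0.714 with 67 missing, and the apparent tipping point is about 15 to 16% instead of 21 to 22% among missing predicted non-responders. The crossing below 0.65 at a rate of 1/6 is conditional. The structural distortion does not depend on it.

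These sizes rest on the plan's sensitivity, specificity and 5:1 ratio, on missing patients sharing the completers' 20% predicted-responder share, on a single reader, and on random allocation as inferred from the footnote.

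**What to change.** Replace the one-way Figure 6 with a two-way grid: imputed response rate among missing predicted responders on one axis, and among missing predicted non-responders on the other. Mark the observed PPV and 1 - NPV as the missing-at-random reference. Use expected counts or repeated draws instead of one random allocation, and state the rule in SAP 2.3. Present the grid by reader and mark the region where the same two of three readers still reject both null hypotheses, since that is the success rule in SAP 1.3. The cost is SAP wording and re-programming of Figure 6, with no new data.

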2.4 Interim Analyses

There are no interim analyses planned for this study.

2.5 Calculation of TUV

TUV_{joint} is defined to be the mean pixel intensity of the region of interest (ROI) defined by the reader divided by the mean pixel intensity of the hand reference region. Each of the three blinded readers will have determined the TUV distribution for both anterior and posterior views of the wrists and hands (wrists, MCPs, and PIPs) for the healthy patient normative data set. For all of the following calculations, the reader-specific TUV_{joint} limits will be used. The upper

limit of normal is defined to be the upper limit of the 95% prediction interval of the joint-and-view-specific TUV in the normative data set.

For each RA patient do the following.

Step 1: Calculate TUV_{joint} for each of the 22 DAS28 joints for which data are collected.

Step 2: Identify all imaged joints with $TUV_{joint} > upper limit of normal for the anatomically similar joint and view. These will be referred to as inflamed joints (IJ). Each joint has an anterior and posterior view: a joint is considered an IJ if either view has a <math>TUV_{joint}$ higher than the upper bound from the normative data set.

Step 3: Calculate the macrophage-involved contribution (MI) to Tc 99m tilmanocept localization for each IJ. This is done by expressing the TUV for the IJ as a fractional change from the mean TUV for the anatomically equivalent joint and view. That is, if TUV_{joint} and \overline{H}_{joint} represent the joint and view specific TUV and the mean TUV for the anatomically equivalent joint and view from the normative data set respectively, the macrophage contribution to TUV is MI_{joint}:

$$MI_{joint} = \frac{TUV_{joint} - \overline{H}_{joint}}{\overline{H}_{joint}}.$$

Step 4: TUV_{global} is the total of the macrophage-involved contributions for the IJs. (Note that MI_k is effectively 0 if TUV_{joint} is less than or equal to the upper limit of normal from the normative data set.) That is,

$$TUV_{global} = \sum_{All IJs} MI_{IJ},$$
$$TUV_{global} = \sum_{k=1}^{22} MI_k.$$

The change in TUV_{global} (Δ TUV_{global[5w]}) is the Δ % from baseline:

$$\Delta TUV_{global[5w]} = 100 \cdot \frac{TUV_{global[5w]} - TUV_{global[b]}}{TUV_{global[b]}}.$$

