4.0 Analysis of Efficacy

4.1 Description of Efficacy Variables

4.1.1 Definition of Responder/Non-Responder Status

4.1.1.1 Prediction Algorithms

The following two prediction algorithms will be defined for use in evaluating primary and secondary efficacy. Each algorithm will be used to predict a clinical response, and the subsequent prediction will be compared to the actual observed clinical response as described in Sections 4.1.2 and 4.1.3. In addition to these two prediction algorithms, the use of TUV_{global[b]} alone for the prediction of non-response will be analyzed as the key secondary efficacy variable. If TUV_{global[b]} is < 5 then the prediction is N (no improvement), otherwise, prediction is Y (improvement).

The $\Delta TUV_{global[5w]}$ values will be used to predict improvement at 12 and 24 weeks according to algorithm 1. The $\Delta TUV_{global[12w]}$ values will be used to predict improvement at 24 weeks according to algorithm 2. Both algorithms will be applied after the change in TUV calculations have been rounded to the nearest integer percentage (i.e., nearest hundredths place for a proportion).

1. ∆TUV_{global[5w]} bucketing

In the below, TUV_{global} represents the global TUV at the current time point and $TUV_{global[b]}$ represents the global TUV at baseline:

- If TUV_{global[b]} is < 5 then the prediction is N (No improvement)
- Else if

$$\Delta TUV_{global[5w]} = \frac{TUV_{global[5w]} - TUV_{global[b]}}{TUV_{global[b]}} \le -0.10$$

the prediction is Y (patient has improved). That is, a patient will be predicted as improved if TUV_{global} goes down by greater than or equal to 10%.

- Otherwise, the prediction is N.
- 2. $\Delta TUV_{global[12w]}$ bucketing

In the below, TUV_{global} represents the global TUV at the current time point and $TUV_{global[b]}$ represents the global TUV at baseline:

- If TUV_{global[b]} is < 5 then the prediction is N (No improvement)
- Else if

$$\Delta TUV_{global[12w]} = \frac{TUV_{global[12w]} - TUV_{global[b]}}{TUV_{global[b]}} \le -0.10$$

the prediction is Y (patient has improved). That is, a patient will be predicted as improved if TUV_{global} goes down by greater than or equal to 10%.

• Otherwise, the prediction is N.

Tables which display the concordance between the predictions from each algorithm vs. clinical assessment will be provided. A listing showing which algorithms provide a prediction of improvement vs. no improvement, by patient, will also be provided.

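### SAP 2.5 does not match joints across visits, so an inflamed joint that is unmeasurable at Week 5 counts as healed and can by itself produce a predicted response

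*SAP*

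**What the plan says.** SAP 2.5 builds TUV_global in four steps.

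- "Step 1: Calculate TUV_{joint} for each of the 22 DAS28 joints for which data are collected".
- Inflamed joints are then chosen: "Step 2: Identify all imaged joints with" a value above the upper limit of normal for that joint and view. Exceeding the limit in either view is enough.
- Each inflamed joint receives an MI, its fractional excess over the healthy mean for the same joint and view.
- TUV_global "is the total of the macrophage-involved contributions for the IJs". It is a plain total, also written as a sum over k = 1 to 22. The only zero stated is for a joint whose TUV "is less than or equal to the upper limit of normal from the normative data set".

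The Week 5 change is the percent difference between the two totals. SAP 4.1.1.1 predicts no improvement when the baseline total is below 5. Otherwise it predicts improvement if TUV_global "goes down by greater than or equal to 10" percent. On rounding it says: "Both algorithms will be applied after the change in TUV calculations have been rounded to the nearest integer percentage".

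Protocol 9.5.5 leaves missing TUV data to the SAP. The SAP 2.3 table has two rows on TUV, both at patient level. One is for a patient who has a baseline total of at least 5 "but is missing week 5 imaging data", whose prediction is imputed. The other is for a patient with no baseline TUV_global, whose prediction is set to missing. Neither row mentions a single joint or view.

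**The concern.** Because TUV_global is a sum and not a mean, its value depends on how many joints could be measured. A joint without a usable measurement cannot be selected as inflamed, so it drops out of the total and looks the same as a joint that has returned to normal. If the measurable set differs between baseline and Week 5, the percent change mixes a change in uptake with a change in which joints were counted.

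The prediction feeds both co-primary endpoints. A joint lost at Week 5 pushes the patient towards a predicted response. In a clinical non-responder that costs specificity; in a clinical responder it adds to sensitivity. The baseline total also decides the key secondary endpoint (NPV of the baseline value alone), so a joint lost at baseline can move a patient into the predicted non-responder group there.

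The plan also treats neighbouring cases differently. A Week 5 scan that is missing altogether gets an imputed prediction, whereas under the formula a scan missing part of a hand is scored as if those joints had healed. The tipping-point analyses in SAP 2.3 vary only values that were treated as missing, so they would not show this.

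**Working it through.** **The plan's own figure.** SAP 1.3 gives 98 clinical non-responders (specificity 0.92 against 0.80) and 100 clinical responders (sensitivity 0.80 against 0.65) for 90% power each, with an exact binomial test at one-sided 0.025 and a single reader. This reproduces:

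- n = 98: reject at 87 or more correct, alpha 0.0158, power 0.908.
- n = 100: reject at 75 or more correct, alpha 0.0211, power 0.913.

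The sample size is not affected by this point.

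**Effect of one lost joint at Week 5.** Inputs are the sum and change formula (SAP 2.5) and the cut-off and rounding (SAP 4.1.1.1). Suppose joint j is inflamed at baseline and unmeasurable at Week 5, and every other joint is unchanged. Then

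change (%) = −100 × MI_j / TUV_global[b].

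The prediction becomes improvement when this rounds to −10 or lower, so joint j must hold about 9.5% of the baseline total (10% without rounding).

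- Baseline total 5: MI_j of about 0.095 × 5 = 0.475 (0.50 unrounded).
- Baseline total 10: MI_j of about 0.95 (1.0 unrounded).

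**Number of inflamed joints, k.** The largest contributor holds at least 1/k of the total. With k of 10 or fewer, that is at least 10%, so losing that joint is always enough. If contributions are equal, losing any one inflamed joint gives −100/k: −20% at k = 5, −10% at k = 10, −9.1% at k = 11 and −4.5% at k = 22. From k = 11 upwards, one loss is not enough on equal shares. It becomes enough if uptake is uneven or the other joints also fall. With a 5% fall elsewhere, the share needed drops to 1 − 0.905/0.95 = 4.7%.

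**Worked example (assumed values).** Twelve inflamed joints, one with MI 0.6 and eleven with MI 0.4: baseline total 0.6 + 11 × 0.4 = 5.0. The 0.6 joint cannot be measured at Week 5 and nothing else changes.

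- As written: 4.4 against 5.0 is −12%, a predicted responder.
- On the joints measured at both visits: 4.4 against 4.4 is 0%, a predicted non-responder.

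**Loss at baseline.** A true total of 5.4 that loses a joint with MI 0.5 is recorded as 4.9. That is below 5, so the prediction is automatically non-response. If the total stays at 5 or above, the joint's reappearance at Week 5 can hide a real fall.

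**Loss of one view.** If the remaining view still exceeds its own limit, the joint stays in the total. The loss matters only if it removes the joint or changes its MI.

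**Possible consequence (assumed rates, single reader).** Let q be the share of correctly predicted non-responders flipped to a predicted response, so that specificity is 0.92 × (1 − q):

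| q | Specificity | Power, n = 98 | Power, n = 500 |
|---|---|---|---|
| 0 | 0.920 | 0.91 | > 0.99 |
| 1% | 0.911 | 0.84 | > 0.99 |
| 2% | 0.902 | 0.74 | > 0.99 |
| 3% | 0.892 | 0.64 | > 0.99 |
| 5% | 0.874 | 0.41 | > 0.99 |

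For sensitivity, take a true value at the null of 0.65 and flip 5% of the false negatives: 0.65 + 0.35 × 0.05 = 0.6675. The chance of passing that one test at n = 100 rises from 2.1% to 4.8%. None of these flip rates comes from the documents.

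**The case against.** The strongest reply is that the SAP never says an unmeasured joint scores zero. Protocol 8.4.2 calls for a TUV for each of the 22 hand and wrist joints, so the closing words of Step 1 may simply name those 22 out of the 28. On that view, a sum over 22 terms with one term absent could be called undefined, TUV_global would be missing, and the SAP 2.3 rows would apply. The Week 5 row also does not say that the whole scan must be missing. Part of this stands: zero is a result of the formula and not an expressed rule. But the SAP does not say that an incomplete set makes the total missing, and the selection of inflamed joints from imaged joints still yields a number. Two programmers could reasonably derive different predictions for the same patient.

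Other protections are partial. Excluding hand or wrist amputation and arthroplasty limits permanently absent joints but not imaging failures. Table 5 and Data Listing 27 would let a reader see incomplete joints, but they do not change the prediction. The rule that two of three readers must succeed does not reliably help, because all three read the same images.

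A reader might infer more than the documents support:

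- **That any patient with 10 or fewer inflamed joints is flipped by one unreadable joint.** This needs equal contributions, a baseline total of at least 5, a lost joint that was inflamed, and no offsetting rise elsewhere. Without equal contributions it holds only for a joint with a large enough share.
- **That the error runs one way.** Week 5 losses push towards predicted response and baseline losses mostly the other way. No net direction is shown.
- **That losing one view has the same effect as losing the joint.** The either-view rule gives some protection.
- **That the co-primary endpoints in practice measure image completeness.** The documents give neither a rate of unmeasurable joints nor a distribution of MI.

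**Conclusion.** The concern holds as a defect in a stated formula. SAP 2.5 compares totals that may be built from different joints, and no passage clearly covers a partly readable scan. Under the formula, losing one inflamed joint at Week 5 is sufficient by itself for a predicted response, provided that the baseline total is at least 5, the lost joint held about 9.5 to 10% or more of it, and the remaining joints are unchanged.

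The effect on the trial's sensitivity and specificity cannot be sized from the documents. At the minimum of 98 non-responders, even a 2% flip rate would cost noticeable power for specificity (0.91 to 0.74). At the 500 expected under the 5:1 ratio it would not, and the remaining issue would be some inflation of apparent sensitivity. Both statements rest on assumed flip rates. The case for acting is that the error is avoidable at little cost and can be settled before anyone knows which patients it affects.

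**What to change.** In SAP 2.5:

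- Compute the Week 5 percent change with numerator and denominator summed over the same joint-and-view pairs, namely those measurable at both visits.
- If the matched baseline sum is zero, or fewer than a pre-specified number of joints are evaluable, treat the patient as missing Week 5 imaging data under SAP 2.3. The sponsor should set that number before unblinding to the results.
- For the baseline cut-off, count an incomplete sum of 5 or more as 5 or more, since the unmeasured joints could only add to it. Let an incomplete sum below 5 keep its non-response prediction in the primary analysis, with a sensitivity analysis setting it to missing. Setting all such patients to missing in the primary analysis would needlessly remove them from the ITD and NPV analyses, including those whose sum is far below 5.
- List the affected patients by reader and visit, and report the current unmatched sum as a sensitivity analysis.

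The cost is SAP wording and some extra derivation work. Per-joint and per-view TUVs are already planned for Table 5, so no new data are needed. A few more predictions will be imputed. For affected patients the change will be measured on a subset of joints, while the baseline cut-off still uses all joints measured at baseline. Protocol 3.1 says the value of 5 came from NAV3-31. The documents do not show how the cut-offs perform on a subset of joints, which is one reason to keep the current sum as a sensitivity analysis.
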